10.2 SAMPLE SIZE DETERMINATION

A total of 32 subjects will be enrolled accounting for a 10% of loss of follow up. Sample size is based on 80% power to detect a difference in change from baseline to day 5 (or death whichever comes first) in mtDNA. With 16 subjects in the placebo arm and 16 subjects in the iCO arm, we will have 80% power to detect a 17225 absolute difference in change in mtDNA (copies/ μ l) from baseline to day 5 (or death whichever comes first) between treatment arms, assuming a conservative 14011 standard deviation (SD)¹⁶⁶ (Table 4). We will also have 80% power to detect a 0.98 difference in LIS, 81 mm Hg difference in PaO₂/FiO₂, and a 0.147 difference in Vd/Vt between treatment arms, assuming an SD of 0.8, 66, and 0.12 respectively^{167,168} (Table 5). With 16 patients randomized to iCO (Table 6), there will be a 77% probability of observing at last one AE that has a 10% background rate and a 96% probability of observing at least one AE that has a 20% background rate.

With 16 patients to each arm, we demonstrated differences in proportions with 2-sided 5% alpha (Table 7).

Table 4. Minimal Detectable Difference at 80% Power for Primary Outcome

Endpoint	Expected Mean Change in Placebo Arm	Expected Mean Change in iCO Arm	Standard Deviation	Detectable Absolute Difference (alpha=5%)
Change in mtDNA (copies/ μ l)	13348	-3877	14011	17225

Table 5. Minimal Detectable Difference on Day 7 at 80% Power for Secondary Endpoints

Endpoint	Detectable Absolute Difference on Day 7 (alpha=5%)	Standard Deviation
LIS	0.98	0.8
PaO ₂ /FiO ₂	81	66
OI	12.4	10.097
Vd/Vt	0.147	0.120
Vasopressor free days	5.2	4.2
Ventilator free days	13.7	11.2
ICU free days	12.6	10.3

Table 6. Probability of observing 1 or more events on the iCO arm for different background AE rates.

n	Background AE rate	Probability to detect ≥ 1 AE
16	0.010	0.13
16	0.020	0.25
16	0.035	0.39
16	0.050	0.51
16	0.100	0.77
16	0.150	0.90
16	0.200	0.96

Table 7. Adverse Events: Differences in proportions that can be demonstrated with 16 on each arm, 2-sided 5% alpha.

Placebo Proportion	iCO Proportion	Difference	Power
0.40	0.0191	0.3809	0.80
0.40	0.0042	0.3958	0.85
0.40	0.0000	0.4000	0.90
0.45	0.0459	0.4041	0.80
0.45	0.0293	0.4207	0.85
0.45	0.0103	0.4397	0.90
0.50	0.0762	0.4238	0.80
0.50	0.0580	0.4420	0.85
0.50	0.0370	0.4630	0.90

PASS version16, test for two proportions, unpooled
variance

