10.4.3 ANALYSIS OF THE SECONDARY AND EXPLORATORY ENDPOINTS

LIS, PaO₂/FiO₂, oxygenation index (OI), dead space fraction (Vd/Vt), and SOFA will be analyzed using repeated measures analysis of covariance (ANCOVA) to assess the effects of treatment, time, and the interaction between time and treatment, while incorporating between-patient variation in baseline measurements and important covariates including severity of ARDS (SAS PROC MIXED). Interaction contrasts will include polynomial trends

across time, focusing on a linear trend suggesting improvement and a quadratic trend suggesting that improvement is leveling off. As part of our analysis, we will also include the interaction between treatment and ARDS severity in the model. Because the study is not powered for the interaction between treatment and severity of ARDS, this test will be exploratory. We will also perform post-hoc analyses within each severity group to generate hypotheses for future study. For analysis of secondary endpoints, we will compare biological outcomes between treatment arms using the Mann-Whitney U or t-test for numerical endpoints and either χ^2 or Fisher's exact test for categorical outcomes.

Based on our prior work^{3,169}, the SD of the log-IL-18 is approximately 0.7. With 16 subjects in the placebo arm and 16 in the iCO arm, we will have > 80% power ($\alpha = 0.05$) to detect a difference in IL-18 levels of 0.5 log which corresponds to a 1.65-fold difference in plasma IL-18.

Based on an interim analysis of Cohort 1 in our Phase I trial, we will also have >80% power to detect a difference in a number of LM and SPMs including PGD₂, PGE₂, PGF_{2 α} , TXB₂, RvD2, and Mar1. Briefly, for multivariate statistical analysis, partial least square discriminant analysis (PLS-DA) will be performed as we have done previously¹⁷⁰. As we are testing multiple secondary and exploratory endpoints, a conservative 1% α level (ie. $p < 0.01$) will be used to accept statistical significance.

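### Section 10.2: Tables 4 and 5 do not follow from 16 per arm at alpha 5%, and Table 5 is not computed at the 1% level used for the secondary endpoints

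*Combined protocol and SAP*

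**What the plan says.** Section 10.2 sets the enrolment: "A total of 32 subjects will be enrolled accounting for a 10% of loss of follow up". It then gives the basis: "Sample size is based on 80% power to detect a difference in change from baseline to day 5". With 16 subjects in each arm, "we will have 80% power to detect a 17225 absolute difference in change in mtDNA", for an SD of 14,011. Table 4 lists expected mean changes of 13,348 (placebo) and −3,877 (iCO), and heads the detectable difference with alpha 5%.

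For secondary endpoints the same section says "We will also have 80% power to detect a 0.98 difference in LIS", with similar statements for PaO2/FiO2 and Vd/Vt. Table 5 extends this to OI and to vasopressor-, ventilator- and ICU-free days, again headed alpha 5%. Tables 6 and 7 (adverse events) are labelled 16 per arm. Two-sidedness is stated only for Table 7: "we demonstrated differences in proportions with 2-sided 5% alpha".

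Section 10.4.2 names the Mann-Whitney U test for the primary endpoint without giving a significance level. Section 10.4.3 plans repeated-measures ANCOVA for LIS, PaO2/FiO2, OI, Vd/Vt and SOFA, and sets the threshold: "As we are testing multiple secondary and exploratory endpoints, a conservative 1" per cent level, that is p < 0.01.

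**The concern.** A detectable difference of about 1.23 SD is too large for 16 per arm at 5% and 80% power; one would expect about 1.02 SD. The same ratio recurs in every row of Table 5, so this is not a single typing error. At least one of the printed n, alpha or power is not the value behind the tables, and a reader cannot tell what the sample size justification is.

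The secondary endpoints raise a second issue. Their detectable differences are quoted at 5%, but results will be judged at 1%. Sections 10.2 and 10.4.3 give no detectable differences for LIS, PaO2/FiO2, OI or Vd/Vt at the level that applies, so the 80% figure does not describe the test that will decide them.

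**Working it through.** **Inputs.** Differences and SDs are from Tables 4 and 5; 16 per arm, 10% loss and 80% power from Section 10.2; 1% from Section 10.4.3. Two-sided testing is assumed for Tables 4 and 5. One-sided 5% would make the detectable differences smaller still and widen the gap. Evaluable n: 16 × 0.9 = 14.4, taken as 14 per arm; conversely 14/0.9 = 15.6, rounded up to 16.

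**Formula.** Two-sample t-test with n per arm and δ = difference/SD. Power = P(T > t(1−α/2; 2n−2)), where T is noncentral t with 2n−2 df and noncentrality δ√(n/2).

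**Primary endpoint.** 13,348 − (−3,877) = 17,225, and δ = 17,225/14,011 = 1.2294.

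- 16 per arm, 5%: t = 2.042, noncentrality 1.2294 × √8 = 3.477, power 0.920. The 80% detectable difference is 1.0237 SD = 14,343.
- 14 per arm, 5%: t = 2.056, noncentrality 1.2294 × √7 = 3.253, power 0.879. The 80% detectable difference is 1.1001 SD = 15,413.
- Mann-Whitney, simulated with normal data (20,000 runs): about 90% at 16 per arm and 85% at 14.

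The stated 80% is not reproduced at 5% with either n.

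**Which inputs would fit Tables 4 and 5?**

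- 14 per arm, two-sided 2.5%, 80% power: 1.2252 SD. LIS 0.980, PaO2/FiO2 80.9, OI 12.37, Vd/Vt 0.147, ventilator-free days 13.72, ICU-free days 12.62. Vasopressor-free days comes to 5.146 against the printed 5.2. Power at 17,225 is 80.3%.
- 15 per arm, two-sided 5%, 90% power: 1.2264 SD. All seven Table 5 rows match after rounding (vasopressor-free days 5.151). Power at 17,225 is 90.1%.
- 13 per arm, 5%, 85% power: also 1.2252 SD.

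Several combinations fit, and none is 16 per arm at 5% with 80% power.

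**Tables 6 and 7 as a check on n.** Table 6 is 1 − (1 − p)^n. At p = 0.10, n = 14 gives 0.771 and n = 16 gives 0.815; the table prints 0.77. All seven rows match n = 14 (0.131, 0.246, 0.393, 0.512, 0.771, 0.897, 0.956) and none matches n = 16 (0.149, 0.276, 0.434, 0.560, 0.815, 0.926, 0.972). For Table 7 (unpooled two-proportion z-test, two-sided 5%), eight of nine rows return the printed 0.80, 0.85 or 0.90 at n = 14, and 0.85, 0.89 or 0.93 at n = 16. The ninth row, 0.40 against 0.0000, lies at the zero boundary; it gives 0.86 at 14 and 0.90 at 16 and carries little weight.

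**Secondary and exploratory endpoints at 1%** (single-day, unadjusted t-test, as Table 5 is framed). For δ = 1.225: at 16 per arm t = 2.750, noncentrality 3.465, power 0.757; at 14 per arm t = 2.779, noncentrality 3.241, power 0.676. The 80% detectable difference is 1.2797 SD (16) or 1.3808 SD (14).

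| Endpoint | Table 5 difference / SD | Ratio | 80% difference at 5%, 16 per arm | 80% difference at 1%, 16 / 14 per arm | Power at Table 5 difference at 1%, 16 / 14 |
|---|---|---|---|---|---|
| LIS | 0.98 / 0.8 | 1.225 | 0.82 | 1.02 / 1.10 | 76% / 68% |
| PaO2/FiO2 | 81 / 66 | 1.227 | 67.6 | 84 / 91 | 76% / 68% |
| OI | 12.4 / 10.097 | 1.228 | 10.3 | 12.9 / 13.9 | 76% / 68% |
| Vd/Vt | 0.147 / 0.120 | 1.225 | 0.123 | 0.154 / 0.166 | 76% / 68% |
| Vasopressor-free days | 5.2 / 4.2 | 1.238 | 4.3 | 5.4 / 5.8 | 77% / 69% |
| Ventilator-free days | 13.7 / 11.2 | 1.223 | 11.5 | 14.3 / 15.5 | 76% / 67% |
| ICU-free days | 12.6 / 10.3 | 1.223 | 10.5 | 13.2 / 14.2 | 76% / 67% |

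**The case against.** Much can be said for the plan. The 10% loss allowance explains how 14 could lie behind figures labelled 16. The 17,225 is simply the difference between the two expected means, so it need not be a solved detectable difference. On the plan's own assumptions the primary comparison has more power than claimed, so N is adequate. Table 5 is openly headed 5% and makes no claim at 1%. The planned secondary analysis is also not a single-day t-test. If the tabled SDs are unadjusted, an assumed baseline correlation of 0.3 would give about 73% (14 per arm) or 80% (16 per arm) at 1%, and 0.5 about 82% or 88%. Section 10.4.3 itself warns that only large changes in the free-day outcomes can be seen.

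Most of this stands, but it does not repair the tables. Fourteen per arm at 5% still gives 88%, not 80%. Table 4's title presents 17,225 as the minimal detectable difference at 80% power. The documents give no correlation from which to claim the ANCOVA gain.

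A reader might go further and infer that the primary test was really planned at 2.5%, so that a p-value between 0.025 and 0.05 would be contestable. The documents do not support that. Section 10 never mentions 2.5%, Table 4 prints 5%, and 2.5% is only one of several back-calculated fits. Nor do they support reading the trial as underpowered for mtDNA.

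**Conclusion.** Tables 4 and 5 are wrong as labelled. At 16 per arm and two-sided 5%, power at 17,225 is 92% and the 80% detectable difference is 14,343; at 14 evaluable per arm they are 88% and 15,413. The offset runs through all of Table 5. Table 6, and all but one boundary row of Table 7, point to n = 14 rather than the labelled 16, but whether n, alpha or power was mislabelled in Tables 4 and 5 cannot be settled from the documents. For the primary endpoint the error is conservative and leaves the printed 5% intact.

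The secondary point is smaller but runs the other way. At p < 0.01, power at the Table 5 differences is about 76% or 68% rather than 80%. This rests on a two-sided, unadjusted, single-day t-test with the tabled SDs; the repeated-measures ANCOVA may do better or worse, depending on correlations the documents do not give.

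**What to change.** 1. Confirm in Sections 10.2 and 10.4.2 that the primary mtDNA test is two-sided at 5%.
2. State enrolled n (16 per arm) and evaluable n (14 per arm) separately, and tie each power statement to one of them.
3. Restate Table 4. At 5% and 14 per arm it should show 88% power at 17,225, or 80% power for 15,413.
4. Recompute Table 5 and the matching sentence in Section 10.2 at alpha 1%, using the 1% column above. If credit is taken for the ANCOVA, state the assumed correlation.
5. Relabel Tables 6 and 7 as n = 14, or recompute them at 16; check the zero-proportion row of Table 7 in either case.

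The cost is wording and table corrections. The stated secondary detectable differences become slightly less favourable (LIS from 0.98 to 1.02 or 1.10, for example). N, the tests and the decision thresholds do not change.

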10.3 POPULATIONS FOR ANALYSES

The primary analysis population will be the modified intention-to-treat (MITT) population. All randomized subjects who complete at least one dose of the study drug will be included in the analysis. Because some patients may withdraw or have a change in clinical status precluding dosing of study drug (eg. post-randomization lactic acidosis), we may randomize additional patients to achieve the enrollment goal of 32 patients who are randomized and treated with at least one dose of the study drug. We expect this to be an uncommon occurrence. Patients who are randomized but do not undergo any study procedures or receive at least one dose of the study product do not contribute any data and will not be included in the study analysis.

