10.4.1 ANALYSIS OF THE PRIMARY SAFETY ENDPOINT

The primary analysis population for the primary safety endpoint will be the MITT population. All randomized subjects treated with at least one dose of the study drug will be included in the analysis.

We will examine AEs by the type of event, as well as by body system class, and we will compare the occurrence of specific AEs in each group, as well as the number of AEs per patient in each group.

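### All seven probabilities in Table 6 are labelled n=16 on iCO but are the values for n=14

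*Combined protocol and SAP*

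**What the plan says.** The sample size paragraph in section 10.2 sets the arms at 16 each: "With 16 subjects in the placebo arm and 16 subjects in the iCO arm". For safety it then says that, with 16 patients on iCO, "there will be a 77% probability of observing at last one AE that has a 10% background rate". For the higher of the two rates cited in the text, the claim is "a 96% probability of observing at least one AE that has a 20% background rate". The supporting table is captioned "Table 6. Probability of observing 1 or more events on the iCO arm for different background AE rates", and its n column reads 16 in all seven rows.

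Three other statements bear on which n applies:

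- Section 10.2 opens with "A total of 32 subjects will be enrolled accounting for a 10% of loss of follow up".
- Section 10.3 (Populations for Analyses) says, on dosing with study drug, that "we may randomize additional patients to achieve the enrollment goal of 32 patients who are randomized and treated with at least one dose".
- The section on analysis of the primary safety endpoint (the second section numbered 10.4.1) says "All randomized subjects treated with at least one dose of the study drug will be included in the analysis".

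**The concern.** The probability of at least one event is a closed formula in the rate and the number of patients, so a table that states both can be checked exactly. For a 10% rate and 16 patients the answer is just over 81%, not 77%. If every row is off in the same direction, the table was probably computed for a different n from the one printed.

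Safety is a primary endpoint (section 4.3). Table 6 is the only statement of what the iCO arm on its own can show about it; Table 7 compares the two arms. Section 9.7.5 adds that no formal between-group testing of adverse events is planned, which leaves more weight on the single-arm statement. A reader judging whether 16 treated patients is an adequate safety sample would use these figures.

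A secondary point is the label on the rate. A background rate is ordinarily the rate expected without the drug. The quantity a safety reader wants is the chance of seeing an event whose true rate on iCO is p. The formula is the same, but the interpretation differs.

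**Working it through.** **Inputs.** n = 16 on iCO (section 10.2 text and every row of Table 6). Rates p = 0.010, 0.020, 0.035, 0.050, 0.100, 0.150, 0.200 (Table 6).

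**Formula.** With independent patients, P(at least one event) = 1-(1-p)^n.

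**Results.**

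| p | Printed (labelled n=16) | 1-(1-p)^14 | 1-(1-p)^16 | Printed minus n=16 value |
|---|---|---|---|---|
| 0.010 | 0.13 | 0.131 | 0.149 | -0.019 |
| 0.020 | 0.25 | 0.246 | 0.276 | -0.026 |
| 0.035 | 0.39 | 0.393 | 0.435 | -0.045 |
| 0.050 | 0.51 | 0.512 | 0.560 | -0.050 |
| 0.100 | 0.77 | 0.771 | 0.815 | -0.045 |
| 0.150 | 0.90 | 0.897 | 0.926 | -0.026 |
| 0.200 | 0.96 | 0.956 | 0.972 | -0.012 |

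For the two figures in the text: 1-0.9^16 = 1-0.1853 = 0.8147, against 0.77 printed; and 1-0.8^16 = 1-0.0281 = 0.9719, against 0.96 printed.

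**Could another n or formula give the printed column?** Of all n from 10 to 19, only n=14 matches all seven rows at two decimals. At n=16 no row matches. The Poisson form 1-exp(-np) fails to reproduce the column as a whole at either n=16 or n=14 (for p=0.10 it gives 0.798 and 0.753).

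**Where might 14 come from?** Taking 10% off 16 gives 16 × 0.9 = 14.4, which rounds down to 14. This is an inference, as neither the text nor the table mentions it.

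**Table 7 as a cross-check.** Table 7 is captioned for 16 per arm and names an unpooled-variance test of two proportions. Its power is approximately Φ(|p1-p2| / √{[p1(1-p1)+p2(1-p2)]/n} - 1.96).

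| Placebo vs iCO | Printed power | n=14 per arm | n=16 per arm |
|---|---|---|---|
| 0.40 vs 0.0191 | 0.80 | 0.800 | 0.850 |
| 0.45 vs 0.0293 | 0.85 | 0.850 | 0.893 |
| 0.50 vs 0.0370 | 0.90 | 0.900 | 0.934 |

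Eight of the nine rows reproduce at n=14. The exception is 0.40 vs 0.0000, printed as 0.90, which gives 0.86 at n=14 and 0.90 at n=16. Both adverse event tables therefore appear to rest mainly on 14 per arm while carrying a label of 16.

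**What a clean iCO arm could exclude.** With 0 events in 16, the exact upper limit solves (1-p)^16 = α. The two-sided 95% limit is 1-0.025^(1/16) = 20.6%. The one-sided 95% limit is 1-0.05^(1/16) = 17.1%.

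**The case against.** The strongest reply is that the figures are sound and only the label is wrong. Section 10.2 allows for 10% loss, 16 less 10% is about 14, and Table 7 fits the same n in eight of nine rows. On that reading there is one unstated assumption, not seven separate mistakes, and relabelling as 14 evaluable of 16 randomized would restore consistency. Replacement of undosed patients is also optional in sections 8.2 and 10.3, and no text guarantees exactly 16 dosed on iCO.

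This probably explains the origin, but it does not make n=14 the right safety denominator. The safety analysis keeps every dosed subject, and the stated goal is 32 dosed. Under section 4.3 the pre-specified events with a time window fall within 6 to 48 hours of dosing and other adverse events are counted through day 7, so later loss to follow-up would not shrink the denominator. As printed, text and table both say 16 and neither is correct for 16.

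The other objections stand as limits on importance. The errors are small and conservative. The sample size rests on mtDNA, and the sections on dosing, analysis and safety oversight make no use of Table 6. The plan speaks only of observing an event and does not claim to detect a drug-caused one, so the point about the background rate concerns wording. The absence of an upper bound for 0 of 16 is not an error.

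**Conclusion.** The concern holds. At the stated n=16, none of the seven Table 6 entries is correct at the printed precision, and all seven equal the n=14 values. The headline figures should be 81% instead of 77% and 97% instead of 96%. The largest error is 5 points, at a 5% rate (0.51 printed, 0.56 correct). The 1% and 20% rows are off by less than 2 points.

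Every error understates the chance of seeing an event, so the plan is slightly better on this measure than it claims. The correction should be made because these are stated operating figures for a primary endpoint, but it does not change the design. The conclusion assumes independent patients with a common rate, and 16 dosed on iCO, as the 1:1 allocation and the target of 32 dosed subjects imply. That the 14 came from a 10% loss allowance is inferred.

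**What to change.** 1. In Table 6, replace the probability column with 0.15, 0.28, 0.43, 0.56, 0.81, 0.93 and 0.97.
2. In the section 10.2 text, change 77% to 81% and 96% to 97%.
3. In the table caption, its column header and the text, describe the rate as the true adverse event rate on iCO instead of a background rate.
4. Recompute Table 7 at 16 per arm, or state the n it uses, so that the two safety tables share one basis.
5. As an optional addition, state that 0 events in 16 would leave a two-sided 95% upper limit of 20.6% (one-sided 17.1%).

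If the authors did intend 14 evaluable patients, the alternative is to print n=14 in Table 6 and the text and explain why dosed patients would drop out of a safety count. The n=16 correction fits the rest of the plan better.

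The core correction costs seven table cells and one sentence. The relabelling, the Table 7 check and the optional bound add a few lines. No data collection, sample size or analysis changes.

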1.3 SCHEMA

TIME-EVENTS SCHEDULE

Measurement/Event	Baseline	Day 1	Day 2	Day 3	Day 4	Day 5	Day 7	Day 14	Day 28	Day 60	6M
Demographic/Admission Data/Medical Hx	X										
Etiology of ARDS	X										
Physical Exam	X										
Height/Body weight	X										
Time on ventilator prior to enrollment	X										
Pregnancy test	X										
Vital Signs (HR, SBP, DBP, MAP, T) ^B	X	X	X	X	X	X	X				
Central venous pressure ^B	A	A	A	A	A	A					
Electrocardiogram (EKG)	X	X	X	X	A	A	X				
Ventilator parameters ^{B, C}	X	X	X	X	X	X	X	X			
Chest X-ray (CXR) review ^D	X	A ^D	A ^D	A ^D	A ^D	A ^D	X				
Lung Injury Score (LIS)	X	X	X	X	X	X	X				
APACHE II Score	X										
SOFA Score ^E	X	X	X	X	X	X	X	X	X		
Glasgow Coma Score (GCS)	X	X	X	X	X	X	X	X	X ^F		
Richmond Agitation Sedation Scale (RASS)	X	X	X	X	X	X	X				
Arterial Blood Gas (ABG)	X										
ABG; Venous Blood Gas if ABG not available ^C		X	X	X	A	A	X	A			
SpO2	X	X	X	X	X	X	X	A			
ScvO2	A	A	A	A	A	A					
Complete blood count (CBC) ^C	X	X	X	X	A	A	A	A	A		
Basic metabolic panel ^C	X	A	A	A	A	A	A	A	A		
PT/PTT/INR ^C	A	A	A	A	A	A	A				
Serum CK, AST, ALT, Albumin, Total Protein ^C	A	A	A	A	A	A	A				
Bilirubin ^C	X	X	X	X	X	X	X	X	X		
Lactate ^C	X	X	X	X	A	A	A				
CO Administration Parameters / Treatment		X ^G	X ^G	X ^G							
Pulmonary Dead Space (Vd/Vt) Measurement		X	X	X			X				
COHb and SpCO		X ^G	X ^G	X ^G							
Vasopressors and inotropes ^B	X	X	X	X	X	X	X	X			
Fluid intake and output ^B	X	X	X	X	X	X					
Renal replacement therapy status	X	X	X	X	X	X	X	X			
Concomitant medications	X	X	X	X	X	X	X				
Adverse event monitoring ^H		X	X	X	X	X	X ^H				
Plasma isolation		X	X	X		X					

Measurement/Event	Baseline	Day 1	Day 2	Day 3	Day 4	Day 5	Day 7	Day 14	Day 28	Day 60	6M
RNA banking		X	X	X		X					
DNA banking – Cell pellet isolation		X	X	X		X					
Primary cell (PBMC) isolation		X				X					
Urine sample collection		X	X	X		X					
Discarded BAL and plasma ^I	A	A	A	A	A	A	A				
Microbiological results ^J	A	A	A	A	A	A	A	A	A		
Vital Status									X	X	X
Discharge Status									X	X	
Ventilator Status									X	X	
Vasopressor Status									X	X	
Neurocognitive Outcomes-MoCA-BLIND, Hayling											X

X - Required

A - When available

B - Data gathered at times indicated or until patient achieves 48 hours of unassisted breathing, whichever is sooner. Data will be obtained pre- and post-treatment on study drug administration days.

C - Measure during reference period (03:00-10:00), obtain at time closest to study drug administration if applicable

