7.1.4 CO MONITORING

The study drug concentration will be monitored continuously with the COventDS built-in analyzer to assure that the accurate dose is delivered. A physician investigator will assess subjects prior to daily iCO treatment. Subjects will have blood drawn daily for measurement of COHb and lactate prior to study drug administration. If COHb \geq 3% (assessed by unblinded physician) or lactate \geq 4 mmol/L, the study drug will be held and the subject will be reassessed for treatment the following day. An electrocardiogram (EKG) will also be performed daily prior to study drug administration to evaluate for cardiac exclusion criteria. Blood COHb levels will be measured with an IL GEM Premier Co-oximeter and SpCO measured with a noninvasive pulse oximeter (Masimo Radical-7).

Blood (arterial or venous) will also be drawn at 20, 60, 75, 90, and 180 minutes for safety monitoring of COHb levels. If an arterial line is not available, venous blood will be used for COHb monitoring as we⁴⁸ and others¹⁴³⁻¹⁴⁵ have shown that venous levels are as accurate and reliable as arterial measurements. Blood (arterial or venous) will also be drawn for blood gas analysis (using the local clinical lab) at 90 minutes or at the completion of treatment, if discontinued sooner than 90 minutes. If arterial blood is not available and venous blood gas is used, PaO₂/FiO₂ will be estimated using the formula $SpO_2/FiO_2 = 64 + 0.84 \times PaO_2/FiO_2$, as long as SpO₂ \leq 97% and subject remains intubated as described in the Statistical Analysis Plan.

The unblinded physician will review and adjudicate COHb measurements and communicate any study drug treatment holds to the administering study staff. COHb levels will be entered into the electronic case report forms (eCRFs) in a separate limited-access project in StudyTRAX by the unblinded RT or physician. The study drug will be administered for up to 90 minutes daily for up to 3 days following randomization or until discontinuation of mechanical ventilation, whichever occurs first.

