9 STUDY ASSESSMENTS AND PROCEDURES

9.1 DESCRIPTION OF STUDY PROCEDURES

Study assessments described below will be done according to the **Time-Events Schedule** in **Section 1.3**.

Vital Signs: Heart rate (beats/min), systemic systolic, diastolic, mean arterial blood pressure (mm Hg), and body temperature (°C), will be recorded in the eCRF.

Central Venous Pressure (CVP): CVP will be recorded if available.

Ventilator Parameters: The following settings will be recorded:

- a) Mode of ventilation
- b) FiO₂ and PEEP
- c) Tidal volume, Respiratory rate (set rate and total rate), Minute ventilation, Inspiratory flow rate
- d) Peak pressure, Plateau pressure, Compliance, and Mean airway pressure. If on a pressure-cycling mode, peak pressure during inspiration will be assumed to be the plateau pressure.
- e) Pressure during inspiration if on a pressure targeted mode (PSV, PCV, etc)

EKG: A 12 lead EKG will be performed and reviewed by a study investigator. The EKG will also be officially read

locally at each site.

Chest X-ray (CXR): The baseline frontal CXR will be reviewed by two study physician investigators to determine study eligibility. Study physician investigators blinded to treatment allocation will review and perform the assessment for the Lung Injury Score (LIS). All 4 lung quadrants will be assessed for infiltrates and pneumothoraces. If the subject is extubated on days 1-5, the study team will order a chest X-ray the day following extubation, if not ordered by the clinical team. Chest X-rays will also be ordered by the study team for endpoint analysis on Day 7, if not ordered by the clinical team.

Lung Injury Score (LIS): The lung injury score will be calculated based on the chest x-ray assessment, PaO₂, FiO₂, PEEP, and ventilator compliance measurement as described in **Appendix E1**.

Oxygenation Index (OI): The OI will be calculated based on the PaO₂, FiO₂, and mean airway pressure obtained from the ventilator parameters.

APACHE II Score: The APACHE II consists of 12 physiological variables, age, and underlying health. The score will be calculated based on the worst values in the 24 hours prior to randomization. Calculation variables are described in **Appendix E2**.

Sequential Organ Failure Assessment (SOFA): The SOFA score will be calculated based on the worst values recorded in the past 24 hours. Calculation variables are described in **Appendix E3**.

- a) Worst PaO₂/FiO₂ for that date

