7.0	2/12/2021	Revision of exclusion criteria #11, #12, and #18. Revision of hypoxia and anemia study drug daily hold parameters.	Revision of hypoxemia, anemia and stroke exclusion criteria may enhance participant enrollment without raising any additional safety concerns.
7.0	2/12/2021	Decrease duration of study drug treatment from 5 days to 3 days.	This will enhance feasibility of the protocol. In phase I, no subjects received 5 days of treatment (median 3.5 days) and circulating mtDNA levels were reduced after 2 doses. In baboons with pneumococcal pneumonia, one iCO treatment attenuated ALI on Day 8.
7.0	2/12/2021	Samples will not be collected on Study Days 4 and 7.	Due to the decreased days of treatment from 5 days to 3 days, blood will no longer be drawn from study participants on days 4 and 7. This will enhance feasibility of the study and decrease blood volume from 136.5 mL to 88.5 mL.
7.0	2/12/2021	Infection control guidelines included for treatment of enrolled subjects with ARDS secondary to COVID-19.	COVID-19 is a common etiology of hypoxic respiratory failure and ARDS. Each site will follow local hospital infection

			guidelines regarding treatment of COVID-19 mechanically ventilated patient with inhaled therapies as well as hospital infection control guidelines regarding blood sample collection/handling.
8.0	10/28/2021	The primary efficacy endpoint was revised to compare the effect of low dose iCO therapy on mitochondrial DNA (mtDNA) levels in patients with ARDS. Effects on Lung injury score (LIS), PaO ₂ /FiO ₂ ratio, Oxygenation Index (OI), and SOFA score were made secondary endpoints. The sample size was changed from 100 to 32 participants. The statistics sections were revised to describe the revised study endpoints.	The Phase I trial of CO in ARDS found significant differences in mtDNA levels. Given the recruitment challenges, the study was repowered based on mtDNA as the primary endpoint. The study endpoints were revised and thus the statistics sections were revised accordingly.
9.0	4/19/2022	The PI was changed from [name] to [name]. [name] was removed as Medical Monitor. The language regarding stratification by site was revised.	[name] is the new PI of the study and will no longer serve as Medical Monitor. [name] will serve as the Medical Monitor. An error was noted in the protocol. The randomization is not stratified by site or any other factor.

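### Day 7 OI, and probably Vd/Vt, exists only for survivors still (or very recently) on the ventilator, so the Day 7 comparison is conditional on survival and ventilation and Table 5's 80% power is not assured

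*Combined protocol and SAP*

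**What the plan says.** Section 10.2 plans 32 patients after allowing for 10% loss to follow-up, and its power statement begins "With 16 subjects in the placebo arm and 16 subjects in the iCO arm". Table 5, titled "Minimal Detectable Difference on Day 7 at 80% Power for Secondary Endpoints", carries a column heading of alpha 5%. It gives OI 12.4 (SD 10.097) and Vd/Vt 0.147 (SD 0.120).

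Section 9.1 calculates OI from PaO2, FiO2 "and mean airway pressure obtained from the ventilator parameters". In the Time-Events Schedule (section 1.3), the ventilator-parameter row carries footnote B: "Data gathered at times indicated or until patient achieves 48 hours of unassisted breathing, whichever is sooner". Vd/Vt is described in section 9.5, for dosing days, as a reading from a NICO or NM3 monitor combined with blood-gas PCO2. Sections 1.3 and 9.6 also list it for Day 7, with no condition on ventilation.

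Extubation before Day 7 is foreseen in sections 3.3.1, 6.5 and 9.1, which provide a chest X-ray after extubation and keep early-extubated patients in the modified intention-to-treat analysis. The only related rule for a physiological value is in section 7.1.4. It allows the SpO2-based PaO2/FiO2 estimate as long as SpO2 is at most 97% "and subject remains intubated as described in the Statistical Analysis Plan".

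Section 10.4.3 analyses OI and Vd/Vt by repeated-measures ANCOVA (PROC MIXED). For the multiple secondary and exploratory endpoints it states that a 1% alpha level "will be used to accept statistical significance".

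**The concern.** A patient liberated on Day 3 who stays off the ventilator has passed 48 hours of unassisted breathing by Day 7 and has no OI. A patient who has died has none either. Whoever remains in the Day 7 contrast was selected by events after randomisation. Sections 3.1 and 3.3.2 name less ventilatory support and better survival as hoped-for effects of iCO, so the selection may differ between arms. Faster liberation would remove the best responders from the iCO arm, and a difference in mortality would remove the sickest patients unequally.

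Two readings are at stake. A null Day 7 result could be judged against 80% power that the number of measured patients does not support. A non-null result could partly reflect who was left to measure.

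**Working it through.** **Inputs.** From Table 5: OI 12.4 with SD 10.097, Vd/Vt 0.147 with SD 0.120, alpha 5%, power 80%. From section 10.2: 16 per arm and 10% loss. From section 10.4.3: alpha 1%. Assumptions: two-sided tests (section 10.2 states this only for Table 7), equal numbers measured in each arm, and the Table 5 SDs holding among ventilated survivors. The number measured per arm on Day 7 is not in the documents and is varied.

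**Formula.** Two-sample t-test with n per arm: d = difference / SD, noncentrality λ = d × √(n/2), df = 2n − 2. Power is the probability that a noncentral t variable falls beyond ±t(1 − α/2, df). The detectable difference is the d that gives 80% power, multiplied by the SD.

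**1. The plan's own figures.** The stated differences are 12.4 / 10.097 = 1.228 SD and 0.147 / 0.120 = 1.225 SD.
- At the labelled inputs (n = 16, alpha 5%) the detectable difference is 1.024 SD: OI 1.024 × 10.097 = 10.34 and Vd/Vt 1.024 × 0.120 = 0.123. Table 5 does not reproduce.
- At n = 14 (16 × 0.9 = 14.4) and two-sided alpha 2.5% it is 1.225 SD: OI 12.37 and Vd/Vt 0.147. The same inputs give LIS 0.980, PaO2/FiO2 80.9, ventilator-free days 13.7 and ICU-free days 12.6, all matching the table after rounding.

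So the printed figures appear to include the 10% loss and an alpha that the table does not declare. They leave nothing for extubation or death.

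**2. Power for OI 12.4 by number measured on Day 7** (Vd/Vt 0.147 agrees to within 0.3 percentage points). Example for n = 8 at alpha 5%: λ = 1.228 × √4 = 2.456, df = 14, critical t = 2.145, power 63%.

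| n per arm (share of 16) | alpha 5% | alpha 2.5% | alpha 1% | 80%-detectable at 5%: OI; Vd/Vt |
|---|---|---|---|---|
| 16 (100%) | 92% | 86% | 76% | 10.3; 0.123 |
| 14 (88%) | 88% | 80% | 68% | 11.1; 0.132 |
| 12 (75%) | 82% | 72% | 58% | 12.1; 0.144 |
| 11 (69%) | 78% | 68% | 53% | 12.7; 0.151 |
| 10 (63%) | 74% | 62% | 47% | 13.4; 0.159 |
| 8 (50%) | 63% | 50% | 34% | 15.2; 0.181 |
| 6 (38%) | 49% | 35% | 22% | 18.1; 0.215 |

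At the printed 5%, a quarter of each arm can lack a Day 7 value before power falls below 80%. At 2.5%, which reproduces the table, there is no margin below 14. At the 1% level, 80% is not reached even with complete data. That shortfall comes from the alpha mismatch, and extubation and death add to it.

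**3. What the model does.** The mixed model uses OI on Days 1-5 and 7 and Vd/Vt on Days 1-3 and 7. Earlier days inform the Day 7 contrast, but the estimate then describes an implied value for patients who have no such value. For Vd/Vt, Day 7 is the only scheduled time point after the treatment days.

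**The case against.** The strongest reply is that nothing in the documents shows the power to be lost. A reader might infer that the stated 80% is simply unavailable. The documents do not support that, because the share ventilated on Day 7 is not given and, at the printed alpha, 12 per arm still gives 82%. Nor does the table assume complete arms, since its figures fit about 14 per arm. Both points stand, and the claim here is only that 80% is not assured.

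Other readings go too far:
- That Day 7 compares only the slowest to recover. Deaths drop out as well, so the group is survivors still, or very recently, ventilated.
- That Phase I shows heavy early extubation. The version 7.0 amendment rationale says no subject received five days of treatment but gives no reason. Drug holds and discontinuations are equally possible.
- That Vd/Vt certainly ceases at extubation. Footnote B is not attached to that row, and no section says so. It is an inference from the monitor method.
- That the treatment estimate is badly biased. The documents give nothing from which to size the bias, and the planned mixed model uses more than the patients observed on Day 7.

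Section 10.4.1 refers to a detailed Statistical Analysis Plan whose text is not in the supplied document, so a handling rule may exist there. It would answer the analysis point but would not correct Table 5. It is also fair that a ranked outcome shifts the question from lung physiology towards survival and liberation, which ventilator-free days and mortality already address. That is why the ranking is proposed alongside the model and does not replace it.

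**Conclusion.** The point holds in limited form. On the protocol's text, Day 7 OI is available only for patients alive and on the ventilator, or at most within 48 hours of leaving it. Vd/Vt very probably behaves the same way. The comparison is conditional on events that treatment may affect, and the supplied text says nothing about how extubation or death enters it.

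The effect on power depends on an unstated number: none of consequence at 12 or more measured per arm with alpha 5%, a fall to 74% at 10, and to 63% at 8. Separately from extubation and death, Table 5's labels do not match its figures, and the plan's own 1% criterion gives 76% at best. These results rest on the t-test, the Table 5 SDs and equal losses in the two arms.

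Severity is low: the trial is sized on mtDNA, and these are two of many secondary endpoints.

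**What to change.** 1. In Table 5, restate the OI and Vd/Vt rows as conditional on being alive and ventilated on Day 7. Show them over a range of expected n, with one declared n and one declared alpha that agrees with section 10.4.3. State whether Vd/Vt is to be attempted after extubation.

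2. In section 10.4.3 and the Statistical Analysis Plan, add a pre-specified Day 7 rank analysis for each of the two endpoints: dead = worst, ventilated = ranked by measured value, alive and off the ventilator = best, with a stated rule for ties. Report it alongside the planned mixed model. Day 7 status can be derived from the unassisted-breathing dates defined in section 1.4 and the date of death. It has to be derived because the schedule collects ventilator and vital status as such only from Day 28.

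Cost: less favourable rows in Table 5 and one added analysis, with no new data collection. The ranked result is not in OI or Vd/Vt units, may have many ties at the best rank, and partly overlaps with ventilator-free days.
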